7.10 SAMPLE SIZE CONSIDERATIONS

Approximately 20 patients with primary CAgD who have a recent history of transfusion will be enrolled.

If the true responder rate is estimated to be 66% and a minimum of 30% is required for success, then with 20 patients, there is 90% probability that the lower limit of the 95% CI will be at least 30%. The minimal observed rate for a successful efficacy claim is $11/20 = 55\%$.

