3.3. Sample Size Justification

Approximately 20 patients with primary CAD who have a recent history of transfusion will be enrolled. If the true responder rate is estimated to be 66% and a minimum of 30% is required for success, then with 20 patients there is 90% probability that the lower limit of the 95% confidence interval (CI) will be at least 30%.

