5.1.4. Handling of Missing Data

Best efforts will be utilized to minimize missing values. If a subject discontinues study treatment early, the subject will be asked to complete study assessments at EOT/safety follow up visit.

For the primary endpoint, which is a composite endpoint of avoidance of transfusion and improvement of Hgb at the treatment assessment timepoint (i.e., Weeks 23, 25, and 26), missing either component results in a missing value for the endpoint. The improvement of Hgb at the treatment assessment timepoint is missing only if no Hgb value is available for all 3 visits (Weeks 23, 25, and 26). Since pre-treatment Hgb is a key requirement to enroll in the study, it is reasonable to assume that all enrolled subjects have at least 1 Hgb prior to the study treatment, which constitutes the baseline Hgb value (see [Section 5.1.1](#)).

For the primary analysis of the primary endpoint, the composite estimand is utilized. Hence, a missing value will be considered a non-response. Other sensitivity analyses specified in [Section 7.2.2](#) will be performed to evaluate the impact of missing values, when appropriate. However, other responder-type endpoints will be analyzed using observed data only.

For the analysis of continuous variables (e.g., secondary endpoints), summary statistics will be computed based on observed data. To analyze lab parameter (e.g., Hgb, bilirubin, LDH) changes attributable to the study treatment (hypothetical estimand), values post any transfusion (after Week 5) or protocol prohibited CAD treatment (defined in [Section 5.1.1](#), after Week 5) will be

censored. The mean change from baseline will be estimated using Mixed Model for Repeated Measures (MMRM) along with its 95% CIs. Multiple Imputation will also be used to estimate the mean change from baseline at treatment assessment timepoint and its associated 95% CI. All these analyses assume missing at random (MAR).

Although the assumption of MAR cannot be verified, the mechanism of missing data due to transfusion or prohibited medication use described below supports such an assumption.

- The protocol (Table 1) specifies the transfusion criteria, which is comprised of the Hgb level.

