5.1.4.1. Mixed-effect Model for Repeated Measures

For normally distributed continuous efficacy endpoints (e.g., lab parameters), a MMRM will be used for the analysis of such endpoints at study visits (including the treatment assessment time points). The MMRM model will include the baseline value of the endpoint and visit. A heterogeneous Toeplitz (TOEPH) covariance matrix within a subject will be used. For the endpoint at the treatment assessment time points (average of Weeks 23, 25, and 26), the estimate will be calculated as the mean of MMRM estimates at Week 23, 25, and 26 visits.

Normality assumptions will be checked using graphical methods. In the event of non-normality, alternative methods will be proposed as an addendum to the SAP prior to the Part A DBL.

The pseudo SAS code for MMRM is as follows:

```
Proc mixed data=(ADaM dataset) method=reml;
  class usubjid visit;
  model chg = base visit / ddfm = kenwardroger solution;
  repeat visit / type=TOEPH subject=usubjid;
  estimate 'treatment assessment timepoint' visit 0 0 0 0 0 0 0
  0 0 0 0 0 0.333 0.333 0.333/cl;
run;
```

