5.1.4.2. Multiple Imputation

The following multiple imputation procedure will be used for continuous endpoints. The regression method with monotone missing patterns will be used for the imputation step (implemented by SAS PROC MI, according to [Rubin 1987](#), pp. 166–167). The pseudo SAS code is provided to substantiate the details of the statistical approach. It does not represent runnable SAS codes for the execution of the analysis, as adjustment to the code is necessary to accommodate the data structure, variable names, and test runs.

1. For endpoints with non-monotone missing data patterns, a Markov chain Monte-Carlo (MCMC) method will first be used to fill in the intermittent missing values.

The pseudo SAS code is as follows, when the input dataset is structured such that variables chg1 - chg11 represent change from baseline at visit Week 1 (Day 7), Week 3, Week 5, Week 7, Week 9, Week 11, Week 13, Week 15, Week 17, Week 19, Week 21, and variable chg_ta represents change from baseline at treatment assessment timepoint:

```
PROC MI data=dat_in seed=1234 SIMPLE NIMPUTE=1 ROUND=1
OUT=dat_mon;
  MCMC IMPUTE=monotone;
  VAR chg1 - chg11 chg_ta;
RUN;
```

2. Missing values will be imputed as the predicted value from a regression model including explanatory variables of the number of transfusions within 6 months prior to study entry (*ntrans*), the value of the same endpoint at baseline (*base*), and change from baseline at all of the previous scheduled visits. The imputation process may be repeated sequentially starting from the earliest visit with missing value (e.g., Day 7) through the treatment assessment timepoint. The forgoing process will be repeated multiple times (i.e., B=100) to generate B imputed datasets.

The pseudo SAS code is as follows:

```
PROC MI DATA = dat_mon SEED=4321 NIMPUTE=100 out=mi_mvn SIMPLE;
  VAR base ntrans chg1 - chg11 chg_ta;
  MONOTONE METHOD=REG;
```

RUN;

- The endpoint of interest (e.g., change from baseline at treatment assessment time points) will be estimated for all B complete datasets.

The pseudo SAS code as follows:

```
PROC MEANS DATA = mi_mvn out=mi_mvn;  
  VAR chg_ta;  
  By _IMPUTATION_;  
ods output statistics=mi_est; RUN;
```

- The method of [Rubin 1987](#) will be used to combine B estimates for the overall estimate and its 95% CI.

The pseudo SAS code is as follows:

```
PROC MIANALYZE DATA = mi_est;  
  MODELEFFECTS mean;  
  STDERR;  
ods output ParameterEstimates=est;  
run;
```

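### The multiple-imputation intervals use a degrees-of-freedom rule that ignores the number of patients: the multiplier is about 1.96 where about 2.12 to 2.18 fits 20 patients (minor; sensitivity analyses only)

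*SAP*

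**What the plan says.** SAP 5.1.4 (Part A) says of the continuous endpoints: "Multiple Imputation will also be used to estimate the mean change from baseline at treatment assessment timepoint and its associated 95% CI". SAP 5.1.4.2 gives the procedure. On the number of imputations: "The forgoing process will be repeated multiple times (i.e., B=100) to generate B imputed datasets". In step 4, Rubin's 1987 method "will be used to combine B estimates for the overall estimate and its 95% CI". The accompanying call, "PROC MIANALYZE DATA = mi_est", carries no EDF= option, and nothing else in the SAP adjusts the imputation interval for sample size. The one small-sample remark on imputation (5.1.4) concerns a possible lack of neighbouring cases under the NCMV restriction.

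The main analysis of the same endpoints does use small-sample degrees of freedom (5.1.4.1): "model chg = base visit / ddfm = kenwardroger solution". On size, SAP 3.3 states: "Approximately 20 patients with primary CAD who have a recent history of transfusion will be enrolled". For bilirubin, SAP 7.3.1 also leaves out patients with Gilbert's syndrome and those whose status is unknown.

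**The concern.** Rubin's 1987 degrees of freedom depend on the number of imputations and on the share of variance due to missing data. They do not depend on the number of patients, because the complete-data degrees of freedom are taken as infinite. Here each imputed-data mean rests on about 20 patients, so 19 degrees of freedom, and fewer for bilirubin.

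SAP 7.1.1 tests nothing beyond the primary hypothesis and reports secondary endpoints as estimates with 95% CIs, so the interval is the inference. The imputation analyses are there to check the MMRM, and a check with large-sample degrees of freedom is not on the same footing as a model with Kenward-Roger degrees of freedom.

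**Working it through.** **The plan's own figure.** The documents give no degrees of freedom or multiplier for these intervals. What they do give is the basis for n: "If the true responder rate is estimated to be 66% and a minimum of 30% is required for success", 20 patients have 90% probability of success, and Protocol 7.10 puts the boundary at 11/20 ("The minimal observed rate for a successful efficacy claim is" 55%). The exact binomial calculation gives a power of 0.897. The Clopper-Pearson lower limit is 31.5% at 11/20 and 27.2% at 10/20. Both figures reproduce, so n = 20 is the right working size.

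**Inputs.**
- Imputations: B = 100 (SAP 5.1.4.2).
- Patients: n = 20 (SAP 3.3). For bilirubin the number is not given; 15 is assumed.
- λ, the share of total variance due to missing data: not in the documents; 0.05 to 0.30 assumed.

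**Formulas.** Let W and V be the within- and between-imputation variances, T = W + (1 + 1/B)V, λ = (1 + 1/B)V/T, and r = λ/(1 − λ).
- Rubin 1987: ν = (B − 1)(1 + 1/r)² = (B − 1)/λ². For λ = 0.05, 99/0.0025 = 39,600; for λ = 0.30, 99/0.09 = 1,100. It can never fall below 99, so the multiplier never exceeds 1.984.
- Barnard-Rubin: with c = n − 1, ν_obs = (1 − λ)·c(c + 1)/(c + 3), and df = 1/(1/ν + 1/ν_obs). For n = 20, c(c + 1)/(c + 3) = 19 × 20/22 = 17.27; for n = 15, 14 × 15/17 = 12.35.

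| n | λ | 1987 df | multiplier | small-sample df | multiplier | ratio |
|---|---|---|---|---|---|---|
| 20 | 0.05 | 39,600 | 1.960 | 16.4 | 2.116 | 0.926 |
| 20 | 0.30 | 1,100 | 1.962 | 12.0 | 2.180 | 0.900 |
| 15 | 0.05 | 39,600 | 1.960 | 11.7 | 2.184 | 0.897 |
| 15 | 0.30 | 1,100 | 1.962 | 8.6 | 2.279 | 0.861 |

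For the same standard error, the planned interval is 7-10% narrower at n = 20 and 10-14% narrower at n = 15.

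**Limiting case with nothing imputed.** This needs no assumption about λ. The interval should then be close to the ordinary t interval, mean ± 2.093 SE at n = 20. As written it is mean ± 1.960 SE (1.960/2.093 = 0.936, about 6% narrower). Its coverage is P(|t₁₉| < 1.96) = 93.5%; at n = 15 it is 93.0%. The Barnard-Rubin rule gives 2.11 here, slightly on the wide side of 2.093.

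**Simulated coverage.** Settings: 6,000 runs each, 100 posterior-draw regression imputations, common correlation 0.6, values missing completely at random. Monte Carlo error is about 0.3 points, √(0.95 × 0.05/6,000).

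| n | predictors | missing | 1987 df | small-sample df |
|---|---|---|---|---|
| 20 | 2 | 2 | 93.7% | 95.4% |
| 20 | 2 | 4 | 94.6% | 96.4% |
| 15 | 2 | 2 | 93.9% | 96.2% |
| 20 | 13 | 1 | 95.6% | 97.2% |
| 20 | 13 | 2 | 97.7% | 98.6% |
| 20 | 13 | 4 | 99.4% | 99.6% |

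The 13-predictor rows match the model coded in SAP 5.1.4.2: baseline, number of prior transfusions and 11 visits. Other runs of that model, with autoregressive correlation and with missingness depending on observed values, stayed between 95.0% and 99.4% under the 1987 df.

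**The case against.** The strongest reply is that the planned procedure has not been shown to under-cover. With 13 predictors plus an intercept, 20 patients and 4 values missing, 16 observed values support 14 coefficients. The between-imputation variance is then so inflated that the 1987 interval covers more than 95%, and adding EDF alone moves it further from nominal. This stands. A reader might infer from the multipliers that the planned intervals are labelled 95% but cover less. The documents do not support that, because the shortfall appears only with nothing imputed or with a small imputation model. With nothing imputed, moreover, there are no missing data to be falsely reassured about.

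A reader might also infer that the imputation results could look more precise than the MMRM only because of the degrees of freedom. That comparison has not been computed. The two standard errors differ for other reasons: the MMRM adjusts for baseline, uses a Toeplitz covariance and averages three visit estimates, while the imputation analysis takes a raw mean.

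Three smaller points also carry weight. The SAP says its code is pseudo code, so the missing option proves little alone; the point rests on the prose naming the 1987 method, and the code adjustments foreseen there concern data structure, variable names and test runs. The one-sample t-test in Protocol 7.3.2 is only a benchmark, since Protocol section 7 gives the SAP precedence. And no formal test depends on these intervals.

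What does not stand is the step from adequate simulated coverage to a correct rule. Two errors that pull in opposite directions happen to offset each other here; repairing the imputation model alone would expose the other.

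**Conclusion.** The point holds as a minor one, with moderate confidence. The stated rule is unsuited to about 20 patients and is inconsistent with the Kenward-Roger choice in SAP 5.1.4.1. For a given standard error the intervals are 7-10% too narrow at n = 20 and 10-14% at n = 15, for λ of 5-30%. Both λ and the bilirubin count are assumptions. With 12 patients and λ = 0.30 the small-sample multiplier would be 2.40, making the planned interval about 18% narrower (1.962/2.397 = 0.819).

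The reach is limited to the imputation sensitivity analyses of bilirubin, FACIT-F, LDH and Hgb. The Clopper-Pearson analysis of the primary endpoint and the MMRM intervals do not change. Actual coverage depends on the imputation model as well, so this is a finding about the degrees-of-freedom rule, not a demonstration that the planned intervals under-cover.

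**What to change.** In SAP 5.1.4.2, step 4, state that estimates are combined by Rubin's rules with Barnard-Rubin small-sample degrees of freedom. Add EDF = (number of patients analysed for that endpoint minus 1) to PROC MIANALYZE: 19 for 20 patients and, for bilirubin, the number left after the Gilbert's exclusions minus 1. Put the rule in the prose as well as the code, because the code is only illustrative.

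The cost is one phrase and one option. Point estimates and standard errors stay the same. Intervals widen by 8-11% at n = 20 (2.116/1.960 to 2.180/1.962) and by 11-16% at n = 15, over the same range of λ. The change is best made together with a smaller imputation model, since EDF alone on the 13-predictor model pushes coverage further above 95%.

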5.2. Data Summaries

5.2.1. Continuous Variables

Continuous variables will be summarized using descriptive statistics including the number of non-missing values (n), mean, standard deviation (SD), median, minimum, and maximum. Where specified in the table shells, the 25th and 75th percentiles will also be provided. Means, medians, and the 25th and 75th percentiles will be presented to one decimal place beyond that with which the data were captured. SDs will be presented to two decimal places beyond that with which the data were captured. Minimum and maximum will be displayed to the same number of decimal places as that with which the data were captured.

Unless impractical within a given table, statistics will be aligned by the decimal place (or assumed decimal place) in the summary tables.

5.2.2. Categorical Variables

Categorical variables will be summarized by counts and percentages. All percentages will be rounded to one decimal place. The percentage will be suppressed when the count is zero. Unless specified otherwise, the denominator for all percentages will be the number of subjects with non-missing data for a given summarization. This number (n) will be included with categorical summaries unless the same variable is also being summarized with descriptive statistics, in which case 'n' will already be provided.

5.2.3. Event Time Variables

Time-to-event variables will be summarized using Kaplan-Meier estimate over time, along with median time to event and probability of an event at specific time points. Partial dates will not be imputed, hence considered unknown. In general, for subjects who do not experience the event, the time-to-event will be censored at the study day of last assessment within a study period (Part A or Part B).

6. STUDY SUBJECTS

6.1. Disposition of Subjects

Subject disposition will be summarized including the number of subjects in the Safety Analysis Set, FAS, PP Set, PK Analysis Set, and PD Analysis Set. The number of subjects with the status of completed, and discontinued study treatment early, including the primary reason for those who discontinued, will be tabulated for Part A. Subject disposition, including the date of the last visit and the reason for early termination for subjects who did not complete the study treatment, will be provided in a data listing.

The number and percentage of subjects attending each visit will be summarized by planned visits for the FAS.

6.2. Demography and Baseline Disease Characteristics

Demographics and baseline disease characteristics will be summarized for FAS.

6.2.1. Demography

Demographic characteristics including age (years), age category (<65, >=65), gender, race, ethnicity, country, geographic location, height (cm), weight (kg), weight category (<75 kg, >=75kg) and body mass index (kg/m²) will be summarized. Geographic locations are defined as Europe, North America, Asia/Japan and other.

6.2.2. General Medical History

A summary of the medical history by system organ class (SOC) and preferred term for FAS will be presented. A subject will be counted only once if they reported one or more occurrences in the SOC and preferred term.

A summary of prior hematological malignancy within the last 5 years and prior thromboembolic history within the last 1 year will be presented.

6.2.3. Baseline Disease Characteristics

Screening and baseline lab parameters, including hematology (such as Hgb, bilirubin, LDH), Gilbert's Syndrome testing, bone marrow biopsy results, and DAT panel, will be summarized based on the FAS. Prior transfusion history (e.g., number of transfusions within 6 months and 12 months of study entry) will also be summarized.

Summaries of prior CAD therapies within the last 5 years, severity of anemia symptoms, and other CAD related diseases characteristics (e.g., presence of acrocyanosis, Raynaud's syndrome, hemoglobinuria, disabling circulatory symptoms, and major adverse vascular events) within 3 months of screening will be presented.

Proportion of subjects who had documented vaccines within 5 years and who have received vaccination during the study will be summarized. The vaccines include meningococcal vaccine, *S. pneumoniae* vaccine, and *H. influenza* vaccine.

6.3. Protocol Deviations

All protocol deviations will be recorded throughout the study. Major and minor protocol deviations/violations are to be pre-specified prior to database lock. All major protocol deviations will be summarized for the FAS. All deviations, both major and minor, will be provided in a data listing.

Important protocol deviations (within Part A study treatment period) impacting efficacy assessment are defined as any of the following:

- Not meeting eligibility inclusion criteria #3,
- Missing at least 2 consecutive doses or 3 intermittent doses,
- Received protocol prohibited CAD treatment ([Section 5.1.1](#)),
- Free of transfusion after Week 5 but missing study assessments at all three visits of Weeks 23, 25, and 26.

Important protocol deviations will be summarized. Subjects who have had any of the important protocol deviations will be excluded from the PP population.

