5.1 INCLUSION CRITERIA

All patients must meet all the following inclusion criteria to be enrolled:

1. Adult males and female patients ≥ 18 years of age at Screening.
2. Body weight of ≥ 39 kg at Screening.
3. Confirmed diagnosis of primary CAgD based on the following criteria:
 - a) Chronic hemolysis
 - b) Polyspecific direct antiglobulin test (DAT) positive
 - c) Monospecific DAT strongly positive for C3d
 - d) Cold agglutinin titer ≥ 64 at 4°C
 - e) IgG DAT $\leq 1+$, and
 - f) No overt malignant disease
4. History of at least one documented blood transfusion within 6 months of enrollment.
5. Hemoglobin level ≤ 10.0 g/dL.
6. Bilirubin level above the normal reference range, including patients with Gilbert's Syndrome
7. Ferritin levels above the lower limit of normal. Concurrent treatment with iron supplementation is permitted if the patient has been on a stable dose during the previous 4 weeks.
8. Presence of one or more of the following CAgD-related signs or symptoms within 3 months of Screening:
 - a) Symptomatic anemia defined as:
 - i. Fatigue
 - ii. Weakness
 - iii. Shortness of breath
 - iv. Palpitations, fast heart beat
 - v. Light headedness, and/or
 - vi. Chest pain
 - b) Acrocyanosis

- c) Raynaud's syndrome
 - d) Hemoglobinuria
 - e) Disabling circulatory symptoms, and/or
 - f) Major adverse vascular event (including thrombosis)
9. Bone marrow biopsy within 6 months of Screening with no overt evidence of lymphoproliferative disease or other hematological malignancy. An additional bone marrow biopsy will be required if the prior bone marrow is deemed unsuitable for analysis by the Sponsor.
 10. Documented vaccinations against encapsulated bacterial pathogens (*Neisseria meningitidis*, including serogroup B *meningococcus* where available, *Haemophilus influenzae*, and *Streptococcus pneumoniae*) within 5 years of enrollment or as specified in [Section 6.1.1.1](#).
 11. Adequate IV access.
 12. If female, must be post-menopausal, surgically sterile, or be established on (≥ 3 months prior to Screening) and agree to continue to use the same highly effective methods of birth control throughout the study and for 9 weeks following administration of the last dose of study drug.
 13. Males must be surgically sterile for at least 90 days or when sexually-active with female partners of child-bearing potential will agree to use highly effective contraception from Day 0 until 9 weeks following administration of the last dose of study drug.

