7.3 EFFICACY - PART A

7.3.1 Analysis populations

Full Analysis Set (FAS): The FAS Population is defined as all patients who received at least 1 dose of study drug.

Per-Protocol (PP) Population: The PP Population is defined as a subset of FAS Population who do not have any important protocol deviations impacting their efficacy assessments.

The FAS analyses will be the primary analyses and the PP analyses will be considered as supportive.

The patients in the FAS population that are excluded from the PP Population will be listed, together with the reason for exclusion from the PP Population.

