3.2. Statistical Hypothesis

The study is designed to test the hypothesis whether patients treated with BIVV009 will achieve a response rate greater than 30%. Statistical hypothesis is written as

$$H_0: \text{response rate} \leq 30\%$$

$$H_1: \text{response rate} > 30\%,$$

where the response rate is the proportion of patients in the intent-to-treat (ITT) population who meet the response criteria defined in Table 2 of the protocol.

Based on discussions with key opinion leaders and experienced clinicians, a response rate of less than 30% is not considered clinically relevant. It is expected that few patients with transfusion dependent primary CAD would meet the responder definition for the primary endpoint without treatment intervention, and as such a null hypothesis of $\leq 30\%$ responder rate for this patient population is reasonable.

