4.2. Per-protocol Set

The per-protocol (PP) population is defined as a subset of FAS who do not have any important protocol deviations impacting their efficacy assessments (defined in [Section 6.3](#)). Selected efficacy endpoints will be analyzed for the PP Population.

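### The Part A per-protocol set tests eligibility on inclusion #3 only, so it can keep patients who break #4, #5 or exclusion #6, criteria that bear on the response endpoint

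*SAP*

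**What the plan says.** Protocol 7.3.1 defines the PP population in general terms: "The PP Population is defined as a subset of FAS Population who do not have any important protocol deviations impacting their efficacy assessments". It names no deviations. Part A SAP 4.2 repeats the definition and sends the reader to SAP 6.3, where deviations "impacting efficacy assessment are defined as any of the following". Four items follow, with no catch-all:

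- "Not meeting eligibility inclusion criteria #3";
- missing two or more doses in a row, or three intermittent doses;
- receiving prohibited CAD treatment;
- being transfusion-free after Week 5 but having no assessment at Weeks 23, 25 and 26.

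The consequence is explicit: "Subjects who have had any of the important protocol deviations will be excluded from the PP population". The per-protocol estimand in SAP Table 3 points back to the same list.

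In Protocol 5.1, #3 is the diagnosis of primary cold agglutinin disease. Criterion #4 is "History of at least one documented blood transfusion within 6 months of enrollment" and #5 is "Hemoglobin level ≤ 10.0 g/dL". In Protocol 5.2, exclusion #6 bars rituximab alone within 3 months, or in combination within 6 months, before enrollment.

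**The concern.** A PP analysis is meant to show whether the result holds in patients who fit the protocol. Two of the omitted inclusion criteria are closely tied to the endpoint. Response needs freedom from transfusion from Week 5 to Week 26, plus Hgb of at least 12 g/dL or a rise of at least 2 g/dL (Part A SAP 7.2). SAP 3.2 defends the 30% null by the kind of patient enrolled: "It is expected that few patients with transfusion dependent primary CAD would meet the responder definition for the primary endpoint without treatment intervention". A patient with no recent transfusion, or with Hgb above the entry limit, does not clearly belong to that group.

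If such a patient were enrolled and responded, the PP response rate would include that response just as the FAS rate does. The supportive analysis would then say nothing about how far the result depends on ineligible patients. In an open-label single-arm study of about 20, deciding after the data are seen whether to exclude such a patient would be hard to defend.

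**Working it through.** **Step 1: the list against the entry criteria.**

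| Entry criterion (Protocol 5.1, 5.2) | In the SAP 6.3 list? | Response component it bears on (Part A SAP 7.2) |
|---|---|---|
| Inclusion #3, diagnosis | Yes | Defines the disease; sets no transfusion or Hgb threshold |
| Inclusion #4, transfusion in the previous 6 months | No | Freedom from transfusion |
| Inclusion #5, Hgb at most 10.0 g/dL | No | Hgb level or rise |
| Exclusion #6, recent rituximab | No | Both, if the earlier treatment is still acting (an assumption) |

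The prohibited-treatment item does not cover exclusion #6. SAP 5.1.1 limits it to the Part A treatment period, whereas #6 concerns the months before enrollment. No other section removes these patients from the PP set. The lead-in to the SAP 6.3 list also confines it to deviations in the Part A treatment period, which fits poorly with any eligibility item, #3 included.

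**Step 2: why 10.0 g/dL matters.** From baseline Hgb b, the smallest rise that meets the Hgb component is min(2, 12 − b).

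- b = 9.0: min(2, 3.0) = 2 g/dL
- b = 10.0: min(2, 2.0) = 2 g/dL
- b = 11.5: min(2, 0.5) = 0.5 g/dL

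At or below 10.0 g/dL the requirement is always 2 g/dL. Above it, the requirement shrinks.

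**Step 3: the plan's own figure.** Inputs from Protocol 7.3.2 and 7.10: n = 20, null 30%, assumed true rate 66%, two-sided 95% Clopper-Pearson interval, minimum success 11/20. The lower limit for x responders out of n is the 2.5% quantile of Beta(x, n − x + 1).

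- 10/20: 27.2%; 11/20: 31.5%. So 11 is the minimum, as stated.
- P(X ≥ 11 | n = 20, 66%) = 0.897, against the stated 90%.
- P(X ≥ 11 | n = 20, 30%) = 0.0171, the exact one-sided error.

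The plan's figure is reproduced.

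**Step 4: illustration.** Assume that 1, 2 or 3 patients broke #4, #5 or exclusion #6, that all of them responded, and that there are no other PP exclusions. The PP set as now written then equals the FAS column. Lower 95% limits are in brackets.

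| FAS, and PP as written | 1 removed | 2 removed | 3 removed |
|---|---|---|---|
| 11/20 (31.5%) | 10/19 (28.9%) | 9/18 (26.0%) | 8/17 (23.0%) |
| 12/20 (36.1%) | 11/19 (33.5%) | 10/18 (30.8%) | 9/17 (27.8%) |
| 13/20 (40.8%) | 12/19 (38.4%) | 11/18 (35.7%) | 10/17 (32.9%) |

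With one such patient, the limit crosses 30% only from exactly 11/20. At the planned 66% rate, P(X = 11) = 10.6%. If the violator is a non-responder, removal raises the limit: 11/20 becomes 11/19 (33.5%).

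**The case against.** The strongest reply is that this is a matter of judgement in a supportive population. Much of that stands.

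- A reader might infer that the SAP contradicts the protocol. It does not. Protocol 7.3.1 lists no deviations, and the opening of Protocol section 7 leaves the details to the SAP and gives it precedence. The supportable statement is that the list leaves out deviations that plausibly affect efficacy.
- A reader might infer that a violator counts as a responder. That does not follow, because every component must be met. A patient who breaks only #4 still needs the full Hgb improvement, averaged over Weeks 23, 25 and 26. A patient who breaks only #5 must still stay transfusion-free.
- A reader might say that the PP analysis passes or fails at 30%. SAP 7.2.1 applies that bound to the composite estimand in the FAS. SAP 7.2.2 only summarises the PP proportion with its interval.
- Violators may not exist. The medical monitor confirms eligibility before enrollment (Protocol 6.1.1.3), and it is rechecked on Day 0 (Protocol 6.1.2). This limits the likely size but does not explain the choice of list, because #3 goes through the same review and is still listed.
- Other outputs help. All deviations are listed and major ones summarised (SAP 6.3). Transfusion history and baseline Hgb are tabulated (SAP 6.2.3). Response is shown by baseline Hgb, prior transfusions and previous rituximab or cytotoxic therapy (SAP 4.6, 7.2.3). With about 20 patients, a reader could recount by hand. However, the subgroup cut-offs (8.5 g/dL; transfusion counts over 12 months; any previous therapy) do not isolate violators, and no planned analysis re-estimates the rate without them.

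**Conclusion.** The gap is real on the text. The list is closed, #3 is its only eligibility item, and breaches of #4, #5 or exclusion #6 do not by themselves remove a patient from the PP set. The omission matters because #4 and #5 bear directly on the response components, and SAP 3.2 rests the null on transfusion dependence.

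The consequence is small. The FAS primary analysis and its success rule are untouched. The number of violators is not given and may be zero. The drop from 31.5% to 28.9% is a knife-edge case that needs exactly 11 responders, one of them a violator. The documents do not support a conclusion that the trial's result is at risk. They do support a cheap improvement that makes the PP check closer to what its definition promises.

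**What to change.** Before the Part A database lock, change the first bullet of Part A SAP 6.3 to read: *Not meeting inclusion criteria #3, #4 or #5 (as assessed for eligibility), or meeting exclusion criterion #6.* State that the restriction to the Part A treatment period does not apply to eligibility items. Keep the FAS as the primary analysis set.

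The cost is one or two lines of SAP text. Hgb, transfusion history and prior CAD therapy are already collected. The PP set may lose a patient or two; with no violators, nothing changes.

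One limit remains. Eligibility rests on the first set of screening laboratory results (Protocol 6.1.1.1), while baseline is the last value before the first dose and must be at least 7 days after any screening transfusion (SAP 5.1.1). An eligible patient transfused during screening can therefore start treatment above 10.0 g/dL. This change would not remove that patient, and should not be presented as if it did.
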